11.1 Adverse Events

11.1.1 Reportable AEs

11.1.1.1 All AEs that occur after the informed consent is signed and baseline assessments are completed (including run-in) must be recorded on the AE CRF (paper and/or electronic) whether or not related to study agent.

How to obtain blood pressure for the study (for study team and participants)

- Use the **wrist blood pressure monitors** provided for the study to record all readings for the study.
- When the blood pressure is being obtained, the participant should sit for at least 5 minutes before taking the blood pressure.
- Place the cuff on participant's wrist as instructed in the wrist blood pressure monitor's manual.
- The arm used to measure blood pressure should be supported and ensure the arm is at heart level.
- The participant should be instructed not to talk during this time, keep their back rested and legs uncrossed.

In the case of an elevated blood pressure, in which it was repeated, the average of the values should be used for Adverse Event determination.

11.1.1.2 AEs not related to surgery that occur from the time of surgery through the 4-5 week post surgery follow-up visit must be recorded on the AE CRF (paper and/or electronic) whether or not related to study agent.

11.1.1.3 All SAEs, including all hospitalizations, during the study period will be reported as per DCP SAE reporting procedures, with the following exception:

Hospitalization for planned surgery will not be reported. However, if this hospitalization event lasts longer than the usual period at the institution (as determined by the Site Principal Investigator or Sponsor), it will be reportable as an SAE. Adverse events (AEs) relevant to the prolongation of this hospitalization will also be collected and reported on AE CRFs.

11.1.2 AE Data Elements:

The following data elements are required for AE reporting.

- AE verbatim term
- NCI Common Terminology Criteria for Adverse Events version 4.0 (CTCAE v4.0) AE term (MedDRA lowest level term)
- CTCAE (MedDRA) System Organ Class (SOC)
- Event onset date and event ended date
- Treatment assignment code (TAC) at time of AE onset
- Severity grade
- Attribution to study agent (relatedness)
- Whether or not the event was reported as a SAE
- Whether or not the subject dropped due to the event
- Outcome of the event

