5.5 Concomitant Medications

All medications (prescription and over-the-counter), vitamin and mineral supplements, and/or herbs taken by the participant will be documented on the concomitant medication CRF and will include: 1) start and stop date, dose and route of administration, and indication. Medications taken for a procedure (e.g., biopsy) should also be included. Medications given in the hospital as part of the standard surgical protocol will not be documented as concomitant medications. However, any medications given to treat an adverse or unexpected event following surgery will be documented.

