9cUAB30 has been evaluated in multiple nonclinical toxicity and safety pharmacology studies sponsored by NCI, DCP. In a 28-day oral toxicity study of 9cUAB30 in rats, target organs were the liver and hematologic system. Dose-dependent increases in liver weight as a percent of brain weight, vacuolation in liver tissue consistent with glycogen deposition, and increased serum aspartate aminotransferase (AST) and alkaline phosphatase (ALP) levels were observed. Hematologic changes included dose-dependent decreases in prothrombin time (PT), increases in fibrinogen, and, at the highest dose (100 mg/kg-bw-day), eosinopenia and neutrophilia. The no observed adverse effect level (NOAEL) was considered to be 3 mg/kg-bw/day. In a 28-day oral toxicity study of 9cUAB30 in female dogs, no treatment-related toxicities were observed even at the highest dose (100 mg/kg-bw/day), which was considered the no observed adverse effect level (NOAEL). In safety pharmacology studies, no cardiac effects were seen in female dogs treated with single doses of 9cUAB30 up to 300 mg/kg-bw/day. Additionally, in a functional observational battery (FOB) study in rats, no effects on central nervous system (CNS) or behavior were seen with single doses of 9cUAB30 up to 100 mg/kg-bw/day. In genotoxicity studies, 9cUAB30 was negative in the *in vivo* mouse bone marrow micronucleus assay and the bacterial reverse mutation test (Ames). In the Chinese hamster ovary (CHO) cell assay, 9cUAB30 did not increase chromosome aberrations or polyploidy after three-hour exposure to low levels of 9cUAB30 in the absence of metabolic activation. However, longer duration (24 hours) in the presence or absence of metabolic activation, or higher doses of 9cUAB30 with metabolic activation, increased chromosome aberrations and polyploidy. Because of variable outcomes and lack of a dose response in the CHO cell assay, 28-day *in vivo* mutagenicity and six-month oncogenicity studies were undertaken in transgenic mice. In the Big Blue *lacI/cII* transgenic mouse mutagenicity study, no dose-related increases in mutation frequency were found in the liver, kidney, or spleen. In addition, 9cUAB30 was not oncogenic in *p53^{+/−}* transgenic mice, and there was no evidence of vitamin A-like toxicity. These results, combined with the negative oncogenicity and mutagenicity data, suggest an acceptable toxicity profile for 9cUAB30.

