7.5 Post-intervention Follow-up Period

7.5.1 7 days after surgery (+/- 1 Day)

- Follow-up telephone contact: the study coordinator will attempt to make contact with the participant at least two times.
- If the coordinator is unable to reach the participant within this time frame a protocol deviation is filed.
- The coordinator will continue his/her attempts to reach the participant until contact is made;
- Concomitant medication review;
- Review adverse events/symptom assessment: if any AEs not related to surgery are concerning to either the participant or the study coordinator/nurse the participant will be scheduled for a clinic visit and evaluation.

7.5.2 4-5 Weeks after Surgery

- Follow-up telephone contact: the study coordinator will attempt to make contact with the participant at least two times.
- If the coordinator is unable to reach the participant within this time frame a protocol deviation is filed.
- The coordinator will continue his/her attempts to reach the participant until contact is made;
- Concomitant medication review;
- Review adverse events/symptom assessment: if any AEs not related to surgery are concerning to either the participant or the study coordinator/nurse the participant will be scheduled for a clinic visit and evaluation.

All participants will receive \$30 for completing the screening visit and \$70 for completing the surgery and returning the blood pressure machine visit as compensation towards the extra efforts taken such as travel expenses, parking, time missed from work or other expenses associated with the study visits. The first 5 participants will be given additional \$50 for the additional time required for the study visit.

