13.6 Reporting and Exclusions

All participants who receive any 9cUAB30 will be analyzed for adverse events. Subjects that maintain 90% compliance for the time period beginning day 1 and ending on the day before surgical intervention will be considered compliant. Compliance will be measured through pill counts conducted by the study coordinator and recorded in the CRF. For biomarker modulation, all participants that have evaluable pre- and post-treatment samples will be included in the analysis. Compliance and availability of evaluable samples for biomarker studies will be included in descriptive statistics.

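### After surgery, an undefined site judgement of relatedness to surgery decides whether a non-serious adverse event is recorded at all

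*Combined protocol and SAP*

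**What the plan says.** Section 11.1.1.1 sets the general rule: "All AEs that occur after the informed consent is signed and baseline assessments are completed (including run-in) must be recorded on the AE CRF". It names no point at which this stops. Section 11.1.1.2 then sets a narrower rule for the post-operative period: "AEs not related to surgery that occur from the time of surgery through the 4-5 week post surgery follow-up visit must be recorded". The AE definition that opens Section 11 takes in untoward events during participation regardless of cause.

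Two routes bring surgical events back in. Section 11.1.1.3 states "All SAEs, including all hospitalizations, during the study period will be reported as per DCP SAE reporting procedures", with an exception for the planned surgical admission. If that admission runs longer than usual it becomes an SAE, and "Adverse events (AEs) relevant to the prolongation of this hospitalization will also be collected and reported on AE CRFs".

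Sections 11.1.2 and 11.1.4 provide for attribution to study agent only. Section 13.6 fixes the safety population: "All participants who receive any 9cUAB30 will be analyzed for adverse events". Section 13.7 plans a descriptive table by severity. Under 5.2 the last dose is taken the day before surgery.

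**The concern.** Before surgery, an event is recorded first and its relation to the agent is assessed afterwards. After surgery the order is reversed: the site first decides whether the event is surgical, and if it is, 11.1.1.2 does not ask for it on the AE form. Dosing runs up to the day before the operation, so agent and surgery are both candidate causes of an early post-operative event. The site knows that every participant took the agent. An excluded event leaves no AE record, so the decision cannot be audited or revised later.

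What is at stake is the completeness of the safety description. The overall goal in Section 1 refers to a non-toxic dose and objective 1.2.7 to overall safety. The human studies described in 2.2.4 and 6.2 were in healthy volunteers and carry no peri-operative experience, so this trial is where such information would first appear. A reader of the 13.7 table could not tell that non-serious events judged surgical had been left out.

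**Working it through.** The point concerns a collection rule. The plan states no figure that depends on it, so there is nothing to reproduce. The check sets the sections side by side.

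1. **Scope of recording.** 11.1.1.1 covers all AEs after consent and baseline, with no end date. 11.1.1.2 covers, from surgery to the 4-5 week contact, only AEs unrelated to surgery. Taken literally the two overlap after surgery and differ. The likely reading is that 11.1.1.2 is an exception to 11.1.1.1, but the text does not say so.

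2. **Who decides, and how.** 11.1.4 gives a five-level scale for relation to the study agent. 11.1.2 lists agent attribution among the required data elements. Neither gives a scale, a criterion or a field for relation to surgery, and nothing says how to handle an event with two plausible causes.

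3. **What is still captured.** SAEs and hospitalizations are (11.1.1.3; the definition in 11.2.1 includes important medical events). So are AEs behind a prolonged surgical stay, and any event that the site judges not surgical. A treated event may also leave a trace under 5.5: "any medications given to treat an adverse or unexpected event following surgery will be documented", on a form that includes the indication. That form does not feed the toxicity table.

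4. **What remains.** Non-serious post-operative events judged surgical are neither required on the AE form nor tabulated under 13.7, even if the plan is followed exactly.

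5. **Possible size.** The documents give no complication rate, so the rates here are assumptions. Let p be the proportion of participants with a non-serious event judged surgical, and n the number treated (36 under 13.1, or 41 if the dose changes).

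   - Expected number = n × p. For n = 36: 36 × 0.05 = 1.8, and 36 × 0.30 = 10.8. For n = 41: 2.1 and 12.3.
   - Chance of at least one = 1 − (1 − p)^n. For n = 36: 1 − 0.95^36 = 0.84 at p = 5%, and 1 − 0.90^36 = 0.98 at p = 10%.

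6. **What a change now could still reach.** The schema says that from November 2021 only ER- participants (12) will be enrolled. The documents do not say how many remained at the January 2022 version. If all 12 did, the expected number is 12 × 0.05 = 0.6 to 12 × 0.30 = 3.6.

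**The case against.** The strongest defence is that this is a deliberate and bounded choice. Operations bring expected complications, and with one arm and controls described as supplying archived tissue only (13.1), a list of such events has no comparator. Objective 1.2.7 compares safety with known retinoid toxicity; the toxicities listed at the end of 8.3 are not surgical complications, and 13.5 makes the comparison qualitative. CBC, INR and PTT are taken on treatment just before surgery, so a coagulation signal can be seen before the operation confounds it. Changing capture at Version 20 would also put participants under two rules. All of this stands. It limits the gain but does not supply the missing definition or reconcile 11.1.1.1 with 11.1.1.2.

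Several stronger readings are tempting, and the documents do not support them:

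- **Surgical complications never enter the safety data.** The SAE and prolonged-stay routes, and the trace under 5.5, rule this out. Capture is inconsistent rather than absent.
- **Section 7.5 applies the same filter.** Its wording, "if any AEs not related to surgery are concerning to either the participant or the study coordinator/nurse", decides who is called in for a clinic visit. The review of AEs and symptoms at both calls is unrestricted.
- **Section 5.5 contradicts 11.1.1.2.** The two set the scope of different forms. A medication can be documented without its indication being a required AE entry.
- **The rat findings point to bleeding.** Section 6.2 says "Hematologic changes included dose-dependent decreases in prothrombin time (PT), increases in fibrinogen". A shorter PT and higher fibrinogen do not suggest bleeding. The dog study showed no treatment-related toxicity, and 6.2 says human metabolism may be closer to the dog's.
- **The trial would claim a false upper bound.** Zero events in 36 would give a one-sided 95% bound of 1 − 0.05^(1/36) = 8.0%, but 13.7 plans only a table and makes no such claim.

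**Conclusion.** The concern holds within limits. From surgery to the 4-5 week contact, non-serious AEs that an open-label site judges surgical need not be recorded or tabulated. The judgement has no stated criteria and no data element. An agent contribution to such events therefore cannot be assessed reliably, because the event may be dropped before agent attribution takes place.

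The size is uncertain: 1.8 to 10.8 of 36 participants, resting wholly on assumed rates of 5% to 30%. This also takes 11.1.1.2 to be an exception to 11.1.1.1, which the text leaves open. Serious events are not affected, and nor are the Ki-67 analysis and its power. With no comparator, fuller capture would make the safety description complete but would not isolate an agent effect. It is a worthwhile, inexpensive improvement, not a threat to the trial's main conclusion.

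**What to change.** - **11.1.1.2:** delete the qualifier that limits recording to events unrelated to surgery, and reconcile the clause with 11.1.1.1, so that all AEs through the 4-5 week contact go on the AE form.
- **11.1.2 and 11.1.4:** add attribution to surgery as a field separate from attribution to study agent, so that an event may carry both.
- **13.7:** tabulate post-surgery AEs with and without those attributed only to surgery.
- **Participants already followed under the current rule:** tabulate them separately and report the limitation.
- **7.5.1 and 7.5.2:** the clinic-visit trigger is a matter for the sponsor and need not change for this purpose.

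The cost is one deleted phrase, one attribution field and a split table, since both follow-up calls already review AEs. The downsides are a longer listing with expected surgical events in it, and a change in capture during the trial.

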11.1.3 Severity of AEs

11.1.3.1 Identify the AE using the CTCAE version 4.0. The CTCAE provides descriptive terminology (MedDRA lowest level term) and a grading scale for each AE listed. A copy of the CTCAE can be found at http://ctep.cancer.gov/protocolDevelopment/electronic_applications/ctc.htm

AEs will be assessed according to the grade associated with the CTCAE term. AEs that do not have a corresponding CTCAE term will be assessed according to the general guidelines for grading used in the CTCAE v4.0. as stated below.

CTCAE v4.0 general severity guidelines:

Grade	Severity	Description
1	Mild	Mild; asymptomatic or mild symptoms; clinical or diagnostic observations only; intervention not indicated.
2	Moderate	Moderate; minimal, local or noninvasive intervention indicated; limiting age-appropriate instrumental activities of daily living (ADL)*.
3	Severe	Severe or medically significant but not immediately life-threatening; hospitalization or prolongation of hospitalization indicated; disabling; limiting self-care ADL**.
4	Life-threatening	Life-threatening consequences; urgent intervention indicated.
5	Fatal	Death related to AE.

ADL

*Instrumental ADL refers to preparing meals, shopping for groceries or clothes, using the telephone, managing money, *etc.*

**Self-care ADL refers to bathing, dressing and undressing, feeding self, using the toilet, taking medications, and not bedridden.

11.1.4 Assessment of relationship of AE to treatment

The possibility that the AE is related to study agent will be classified as one of the following: not related, unlikely, possible, probable, definite.

11.1.5 Follow-up of AEs

All AEs, including lab abnormalities that in the opinion of the investigator are clinically significant, will be followed according to good medical practices and documented as such. AEs with a “possibly”, “probably” or “definitely” attribution to study agent that have occurred prior to surgery will be monitored up to 4-5 weeks after surgery via phone calls.

Participants with AEs “possibly”, “probably” or “definitely” related to study agent that are not resolved at the 4 – 5 weeks post-surgery phone contact, should be referred to their primary care provider for follow-up.

11.2 Serious Adverse Events

11.2.1 DEFINITION: Regulations at 21 CFR §312.32 (revised April 1, 2014) defines an SAE as any untoward medical occurrence that at any dose has one or more of the following outcomes:

- Death
- A life-threatening AE
- Inpatient hospitalization or prolongation of existing hospitalization
- A persistent or significant incapacity or substantial disruption of the ability to perform normal life functions
- A congenital anomaly or birth defect
- Important medical events that may not be immediately life-threatening or result in death or hospitalization should also be considered serious when, based upon appropriate medical judgment, they may jeopardize the participant and may require intervention to prevent one of the other outcomes.

11.2.2 Reporting SAEs to DCP

11.2.2.1 The Lead Organization and all Participating Organizations will report SAEs on the DCP SAE Report Form found at <http://prevention.cancer.gov/clinical-trials/clinical-trials-management/protocol-information-office/pio-instructions-and-tools/2012-consortia>.

11.2.2.2 Contact the DCP Medical Monitor by phone or email (email preferred) within 24 hours of knowledge of the event.

[name], PhD
Breast and Gynecologic Cancer Research Group
Division of Cancer Prevention
[name]
Rockville, MD 200850
Office [contact]
[contact]
Email: [contact]

Include the following information when calling the Medical Monitor:

- Date and time of the SAE
- Date and time of the SAE report
- Name of reporter
- Call back phone number

- Affiliation/Institution conducting the study
- DCP protocol number
- Title of protocol
- Description of the SAE, including attribution to drug

11.2.2.3 The Lead Organization and all Participating Organizations will email (do not FAX) written SAE reports to DCP's Regulatory Contractor CCS Associates, Inc. (CCSA; [contact]) at [contact] within 48 hours of learning of the event using the fillable PDF SAE Report Form.

11.2.2.4 The DCP Medical Monitor and CCSA regulatory & safety staff will determine which SAEs require FDA submission as IND safety reports.

11.2.2.5 The Lead Organization and all Participating Organizations will comply with applicable regulatory requirements related to reporting SAEs to the IRB/IEC.

11.2.3 Follow-up of SAE

Site staff should send follow-up reports as requested when additional information is available. Additional information should be entered on the DCP SAE Report Form in the appropriate format. Follow-up information should be sent to DCP as soon as available SAE's will be followed for 30 days after completion of treatment. Any ongoing SAE's will be referred to the primary care physician for follow-up.

12. STUDY MONITORING

12.1 Data Management

All of the procedures outlined in the University of Wisconsin Chemoprevention Consortium standardized Data Management Plan (approved 09/23/2019) will be followed in this protocol. Please refer to this document for additional details on data management procedures.

This study will report clinical data using the OnCore web-based application clinical trials/database. OnCore will be the database of record for the protocol and is subject to NCI and FDA audit. All OnCore data entry will be performed at the CLO where staff is trained in OnCore per our DMP and applicable regulatory requirements such as 21 CFR; Part 11.

12.2 Case Report Forms

All data entry will be performed by the Consortium lead Organization (or CLO, the University of Wisconsin) staff. Participant data will be entered into protocol-specific electronic case report forms (CRF's), developed from the standard set of DCP Chemoprevention CRF Templates and utilizing NCI-approved Common Data Elements (CDE). PO's will be required to submit data for quality assurance review and entry into the OnCore database within 10 business days of each study encounter. All data entry will be completed by the CLO within 15 business days of the scheduled visit, as defined in the approved master Data Management Plan. Amended e-CRFs will be submitted to the DCP Protocol Information Office for review and approval.

12.3 Source Documents

The CLO will provide participating sites with standardized, pre-printed source document forms that serve a dual role as source documents and as CRF's, which may be used to ensure that all data items are collected. These pre-printed source document forms must be signed and dated by the person completing the form. If the policy at the site mandates the use of an approved local institutional form or source documentation, the local institutional form may be submitted for the forms supplied by the CLO, as long as all required data points are included on the local institutional form. All de-identified source documents will be sent

electronically or by mail to the CLO monitor. All data is due at the CLO within 10 business days of each study visit.

12.4 Data and Safety Monitoring Plan

The standard University of Wisconsin Chemoprevention Consortium DSMP was approved by the DCP on 03/20/2018. In addition to the standard procedures outlined in the consortium DSMP, we will be modifying the DMP and will perform additional monitoring of data for this trial.

12.5 Sponsor or FDA Monitoring

The NCI, DCP (or their designee), pharmaceutical collaborator (or their designee), or FDA may monitor/audit various aspects of the study. These monitors will be given access to facilities, databases, supplies and records to review and verify data pertinent to the study.

